## STUDY PROTOCOL

### A MOBILE PHONE BASED TRIAGE TOOL TO IDENTIFY DISCHARGED TRAUMA PATIENTS IN NEED OF FURTHER CARE IN CAMEROON

#### Protocol Summary

Title	A mobile phone-based triage tool to identify discharged trauma patients in need of further care in Cameroon
Study objectives	
 
1. Establish the feasibility of using mobile phones to follow up on hospitalized trauma patients after discharge in Cameroon.
 
2. Cross-validate a telephone-based triage tool to identify trauma patients who would benefit from further medical care.
 
3. Characterize the impact of timely follow-up on long-term disability and socioeconomic consequences associated with trauma in Cameroon.
 

Study design	
Objective 1: Cohort Study
 
Objective 2: Stepped-wedge intervention, cross-validation of intervention (mHealth telephone triage tool questionnaire) and in-person, blinded physician exam
 
Objective 3: Cohort study

Study sites	
 
1. Laquintinie Hospital of Douala, (Littoral region)
 
2. Limbé Regional Hospital, (Southwest region)
 
3. Pouma Catholic Hospital, (Littoral region)
 
4. Edea Regional Hospital, (Littoral region)
 

Study population	A prospective cohort study of admitted trauma patients in the four-hospital trauma registry
Control arm	Pre-intervention population
Intervention arm	mHealth telephone triage tool implementation
Outcomes	
Aim 1: 1) number and proportion of hospitalized trauma patients who are reached by mobile phone post-discharge.
 
Aim 2: mHealth triage tool score; physician exam determination for “needs further care” or “does not need further care”.
 
Aim 3: Proportion of injured patients who seek clinical follow-up evaluation; GOSE disability level at 2-weeks and at 1, 3, and 6 months

Sample Size	Estimating, that 10% of contacted patients will require further care, a sample size of 1300 patients in the triage cohort will be targeted.
Study duration	24 months

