## 2. STUDY AIMS

The primary study objectives are as follows:

**Aim 1: Establish the feasibility of using mobile phones to follow up on hospitalized trauma patients after discharge in Cameroon.**

*Hypothesis:* Mobile phones are a feasible way of contacting trauma patients after they are discharged from the hospital in Cameroon.

We will contact trauma patients discharged from four hospitals participating in the Cameroon National Trauma Registry at intervals of two weeks, one month, three months, and six months following discharge. The response rate and decay of response over time will be tracked.

**Aim 2: Cross-validate a telephone-based triage tool to identify trauma patients who would benefit from further medical care.**

*Hypothesis:* A triage tool administered over the telephone can effectively identify injured patients who would benefit from further care for their injuries.

An over-the-phone triage tool will be used to predict a binary outcome two-weeks after discharge: needs further care or does not need further care. An independent physician blinded to triage tool outcome who will also render a determination on the same binary outcome, will examine those patients contacted by telephone. Physician assessment will be used as the gold standard to calibrate the model, which will be validated in a separate patient cohort.

**Aim 3: Characterize the impact of timely follow-up on long-term disability and socioeconomic consequences associated with trauma in Cameroon.**

*Hypothesis:* Trauma patients in need of post-hospitalization medical care will have improved disability outcomes if follow-up care is delivered promptly.

Patients will be given a modified Glasgow Outcomes Scale-Extended (GOSE) survey to complete at two weeks, one month, three months, and six months after hospitalization to quantify the death and disability associated with traumatic injury for each patient. Pre- and post-intervention results will be compared.

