**Implementation/Data Collection:** Patients contacted two weeks after discharge will be asked to give additional consent for participating in the triage tool part of the study. Those who consent will be contacted by research assistants and will answer 7-question survey. Patients whose responses trigger concern about the need for further medical attention will be informed that they should return to care and given appropriate instructions. All patients, regardless of triaged status, will be asked to schedule a time for a physical exam and will undergo one either at the hospital or in their place of residence. If patients return to the hospital, compensation for travel expenses will be provided on a sliding scale. This exam will occur within 1 week of the phone interview. Trained study physicians will conduct a structured, standardized exam that will ultimately culminate in a dichotomous outcome for “needs further care” or “does not need further care”. Based on the exam, the physician will determine if the patient would benefit from further services (including additional follow-up care, diagnostic or therapeutic interventions). Additional data will be collected regarding physician opinion as to whether the patient is demonstrating on-trajectory recovery for their age, health status, and injury, and whether the patient is at high, moderate, or low risk for a poor outcome. At the 2-week and 6-month time points, all contacted patients will be asked about their satisfaction with formal medical services, post-injury follow-up care, perceived convenience, and utility of mobile telephone follow-up.

**Figure 1: Step-wedge design of study.** For each site: Diagonal lines depict a GOSE baseline data collection phase, gray arrows depict intervention phase (1 year/site), and black blocks depict follow-up phase (6 months/site).

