**Implementation/Data Collection:** Injured patients who are successfully contacted at any of the study time points following hospital discharge will answer an over-the-phone survey to assess disability using an augmented GOSE (aGOSE) instrument, which is a metric of multi-domain functional status initially targeted for patients following neurologic trauma. It has since been validated in diverse geographic locations and in broader clinical contexts. Additional questions to evaluate economic consequences of injury will be added to the existing GOSE instrument. As our preliminary experience indicates that respondents are extremely reticent to speak directly about money over the phone, indirect measures of economic consequences will be emphasized (**Table**). Respondents will also be asked whether they sought further care for their injuries and if so, whether care was rendered. Six months before we begin using the telephone triage tool we will collect baseline data at all 4 facilities, after which the triage tool will be implemented in a stepped-wedge fashion in the 4 facilities, staggered by three months for each facility's start date. The cohort of patients (or their surrogates) who answer the triage survey will also be asked to answer the aGOSE, which will be administered at 2-weeks and at 1, 3, and 6 months. This design will let us compare intervention patients with historical controls, while controlling for temporal trends.

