**Data Analysis:**

As this study is powered for cross-validation of the triage tool, aim 3 is exploratory in nature and may not detect a difference in validated disability metrics between the intervention control cohorts. Therefore, process improvement indicators will serve as the primary outcome measures for this aim, and disability and economic outcomes will be secondary outcomes. These results will let us calculate effect size for future prospective validation of the triage tool. Summary measures of all outcomes will be calculated using medians and interquartile ranges for numeric and ordinal variables and proportions for binary and categorical variables. Outcome metrics will be stratified by hospital site, injury severity, age, and economic indicators at each time point. Trends in physical and economic disability will be assessed over time. Process outcomes, disability measures, and disability distributions will be compared between baseline and intervention cohorts using Kruskal-Wallis one-way analysis of variance for numerical and ordinal variables and chi-square tests for categorical variables. Univariate linear regression and multiple regression adjusting for age, gender, mechanism, injury severity, and hospital site will be used to assess triage-tool contact as a predictor of GOSE disability

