**Table: Examples of indirect measures of economic consequences**

1. Borrowing or selling household assets as a result of injury
2. Loss of household income as a result of the injury
3. Lost work by any member of the household as a result of the injury
4. Missed school by any member of the household as a result of the injury
5. Household food insecurity as a result of the injury
6. Any member of the household serving as a caregiver for the injured person.

level at 4 weeks, 3 months and 6 months after injury. Triage-tool contact will be evaluated for prediction of economic disability and presentation for follow-up care (both considered as binary variables) using univariate and adjusted multiple logistic regression.

**Outcomes:** Primary outcomes will include proportion of injured patients who seek clinical follow-up evaluation. Secondary outcomes will include GOSE disability level, work lost and other economic consequences of injury, such as spending savings and borrowing money.

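### Aim 3's only named primary outcome is seeking follow-up, which the intervention prompts directly; a rise would show uptake of the recall, not care delivered to patients in need

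*Combined protocol and SAP*

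**What the plan says.** All references are to the combined protocol and SAP.

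- **Outcome.** The Outcomes paragraph of Aim 3 reads: "Primary outcomes will include proportion of injured patients who seek clinical follow-up evaluation". The Protocol Summary lists the Aim 3 outcomes as "Proportion of injured patients who seek clinical follow-up evaluation; GOSE disability level at 2-weeks and at 1, 3, and 6 months". The Aim 3 Data Analysis paragraph gives the ranking: "process improvement indicators will serve as the primary outcome measures for this aim, and disability and economic outcomes will be secondary outcomes".
- **Analysis.** Process outcomes are compared between the baseline and intervention cohorts, with chi-square tests for categorical variables. Triage-tool contact is then related to presentation for follow-up care, as a binary variable, in univariate and adjusted logistic models.
- **Intervention.** Under Aim 2, Implementation/Data Collection: "Patients whose responses trigger concern about the need for further medical attention will be informed that they should return to care". The same paragraph adds: "All patients, regardless of triaged status, will be asked to schedule a time for a physical exam". The exam takes place within a week of the call, and travel is compensated for those who come to the hospital.
- **Receipt of care.** Under Aim 3, Implementation/Data Collection: "Respondents will also be asked whether they sought further care for their injuries and if so, whether care was rendered". No named outcome or model uses the second half of that item.
- **Hypothesis.** In section 2, Aim 3 states that trauma patients who need care after hospitalization "will have improved disability outcomes if follow-up care is delivered promptly".

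**The concern.** The outcome and the intervention are nearly the same act. Telling a patient to return, then counting whether the patient returned, measures compliance with the instruction. A visit at which nothing was needed or given counts the same as a visit at which a complication was treated. The hypothesis is narrower: it concerns patients in need, and care that was delivered.

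The study exam adds a second route. It is part of the intervention phase and is offered whatever the triage result, yet the outcome does not say whether attending it counts as a clinical follow-up evaluation. If respondents report it, seeking rises in the intervention cohort by design.

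The interpretation of Aim 3 is at stake. The Data Analysis paragraph says the results will supply an effect size for a future study. An effect size for seeking describes response to a recall, and nothing planned in Aim 3 turns it into an effect on care received.

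**Working it through.** **The plan's own figure.** The documents give no sample size, power, alpha or effect size for Aim 3. The only related figure is the triage-cohort target set for Aim 2: 13 variables × 10 per outcome category ÷ 0.10 = 1300. It reproduces exactly but does not bear on this point.

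**The text, side by side.**

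| Element | Requires seeking | Requires care given | Requires need |
|---|---|---|---|
| Aim 3 hypothesis (section 2) | – | yes | yes |
| Named primary outcome | yes | no | no |
| Logistic model outcome | yes (presentation) | no | no |
| Survey item | asked | asked | – |

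The gap follows from the text alone. The arithmetic below only shows how large a rise could appear with no added care.

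**Inputs.**
- Flagged share *f*. The only documented tool-flag share is 20/150 = 13.3% (Triage Tool Development). I use 13.7%, the pilot share of physician recommendations (Aim 2, Sample Size), which is close to it. I take 50% as the upper case. That is the newer physician-recommendation share in the Addendum; it is not a tool-flag rate.
- Baseline seeking *b* = 20% or 40%: assumption.
- Compliance *c*, the share of flagged patients who return but would not otherwise have done so, = 20% or 40%: assumption.
- Respondents, baseline/intervention: 300/730 or 600/1300. The 730 and 1300 are the documents' triage-cohort targets. Their use as Aim 3 numbers, and the baseline sizes, are assumptions.
- No extra visit yields care: assumption that defines the scenario.

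**Formula.** Seeking under intervention is p₁ = b + (1 − b)·f·c. With d = p₁ − b, the chance of two-sided p<0.05 is approximately Φ[(d − 1.96·s₀)/s₁]. Here s₀ is the pooled and s₁ the unpooled standard error of the difference, and clustering by hospital is ignored.

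**One case in full** (b = 0.20, f = 0.137, c = 0.40, 600/1300):
- p₁ = 0.20 + 0.80 × 0.137 × 0.40 = 0.2438, so d = 0.0438.
- Pooled rate = (600 × 0.20 + 1300 × 0.2438)/1900 = 0.230.
- s₀ = √[0.230 × 0.770 × (1/600 + 1/1300)] = 0.0208.
- s₁ = √[0.20 × 0.80/600 + 0.2438 × 0.7562/1300] = 0.0202.
- Result: 56%.

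**All cases.**

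| f | b | c | p₁ | 300/730 | 600/1300 |
|---|---|---|---|---|---|
| 13.7% | 20% | 20% | 22.2% | 12% | 19% |
| 13.7% | 20% | 40% | 24.4% | 32% | 56% |
| 13.7% | 40% | 20% | 41.6% | 8% | 10% |
| 13.7% | 40% | 40% | 43.3% | 16% | 27% |
| 50% | 20% | 20% | 28.0% | 77% | 97% |
| 50% | 20% | 40% | 36.0% | >99% | >99% |
| 50% | 40% | 20% | 46.0% | 42% | 69% |
| 50% | 40% | 40% | 52.0% | 94% | >99% |

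With f at 13.3% the upper block runs from 8% to 54%, so the choice between the two pilot shares is immaterial.

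**Study exam.** Suppose the exam counts as follow-up, baseline seeking is 30%, and 30% to 90% of non-seekers attend (both assumptions). Seeking then becomes 0.30 + 0.70 × 0.30 = 51% up to 0.30 + 0.70 × 0.90 = 93%, with no flag acted on at all.

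**The case against.** The case for leaving the plan alone has real weight.

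- **Aim 3 is declared exploratory and has no success threshold.** This stands. A reader might infer that the plan would declare a useless tool successful. The documents contain no rule that would do so; a significant or favourable cohort difference is the most that can arise.
- **Seeking is a legitimate target.** The Background complains that nothing ensures timely follow-up, and the registry description says patients return late. Prompting return is the tool's immediate purpose, so measuring return is reasonable. This stands, and a reading that the primary outcome is simply wrong goes too far.
- **Aim 2 already tests whether flags track need**, against a blinded physician exam, with calibration and ROC curves in a 30% validation group. It is therefore not true that the study as a whole cannot tell a useful tool from indiscriminate recall. But Aim 2 says nothing about whether care was then received.
- **The list is open.** The outcome wording is inclusive and the process indicators are plural, so care rendered could be added. It could, but nothing commits the team to it.
- **The larger probabilities need a large flagged share.** This stands. At about 13% flagged, a significant rise without added care is possible but is far from assured under most of the inputs.

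Two further inferences should be resisted. One is that a test on care rendered would reject only 5% of the time. That follows only from assuming equal care-rendered rates in both cohorts, and it fails if respondents report the study exam as care. The other is that triage question 7 already supplies the answer. It is asked on the same two-week call at which flagged patients are told to return, so it records behaviour before the instruction, and only in triaged patients.

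**Conclusion.** The point holds in a limited form. The only named Aim 3 primary outcome measures uptake of a recall that the intervention itself issues, and it does not exclude a study exam offered to every triaged patient. A rise in it cannot by itself support a statement that follow-up care was delivered to patients in need.

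The size is uncertain. With no added care, the chance of a nominally significant rise is about 8-56% at 13.7% flagged and about 42% to nearly 100% at 50% flagged. These figures rest on assumed baseline seeking, compliance and respondent numbers, and they ignore clustering. The text gap does not depend on them.

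Because Aim 3 is exploratory and seeking is a fair process measure, this calls for an added analysis and restrained wording. It does not call for the primary outcome to be replaced.

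**What to change.** 1. Keep the proportion seeking follow-up, and describe it as a process (uptake) outcome.
2. Beside it, analyse the proportion who sought follow-up care and had care rendered, using the item already in the survey and the same chi-square and logistic models. The Addendum reports the last two-week follow-up in September 2022 and the end of six-month follow-up by January 2023, so label this outcome as added after data collection.
3. State that the study physician exam is excluded from both outcomes. The documents do not say whether the recorded answers separate it from other visits. If they do not, say so and show the results with and without the affected responses.
4. In the intervention cohort, tabulate both outcomes by the physician's determination of need. The plan provides for this exam only alongside the triage tool, so the table describes one cohort and is not a comparison.
5. Base any statement about care delivery, and any effect size for it, on the care-rendered outcome.

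The cost is wording and analysis time, with no new data apart from any effort to identify study-exam visits. Care rendered will have fewer events than seeking, so its interval will be wider in relative terms. It is also self-reported, and the Limitations section promises record checks only where possible; that weakness applies equally to seeking.

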### **INFORMED CONSENT**

We have been collecting trauma registry data in Cameroon since 2008 in collaboration with the Ministry of Public Health. The protocol was reviewed and approved by the Cameroonian Ministry of Public Health, the National Ethics Review Committee in Cameroon, and the Institutional Review Board of the University of California, Los Angeles. Data collection is performed 24 hours per day and seven days per week. After obtaining patients' oral consent, trained staff at each of the four hospital sites collect all relevant information on trauma registry forms, which has a check box to ensure oral consent was given by the patients. At this time, trauma patients are also asked for household mobile phone numbers. If a trauma patient is a child under the age of 21, the mobile phone number of one of her/his parent(s) or guardian(s) is obtained. Where clinically possible, patients are reassured that mobile phone numbers, are being collected for research purposes only.

Two weeks after each trauma patient is discharged, the patient's household is contacted by trained research staff and invited to participate in the study. Consent for participation is obtained orally, over the phone. During this oral consent process, trained research assistants inform potential participants about the purpose of the research, the potential benefits and risks that are involved, and how potential risks are minimized. Potential participants are strongly encouraged to ask questions and have the research staff clarify any information that is not clear. If oral consent is received from the trauma patient or their caregiver the research assistant indicates this by checking a box on the triage tool. To consent to study participation, subjects or caregivers must be over the age of 21 and demonstrate understanding of the study. Households who decline consent are thanked for their time and no further contact is made. All households, regardless of consent status are offered the telephone number of the Cameroon-based Program Manager in the event that they have further questions or comments.

The request for consent as well as any study questionnaires is delivered in the subjects' primary language, either English or French. All research assistants are fluent in both English and French.

### **Data Management**

**Trauma Registry:** Each hospital will require a securely locked, encrypted, password protected computer dedicated solely to trauma registry entry and management. Only the individual hospital trauma registry manager and trauma registry supervisor will have access to the computer. Each hospital will have a secure drop box in which trauma registry instruments may be placed by research personnel after completion. Only the trauma registrars and trauma registry supervisor will have access to the secure drop box. The supervisor will have an additional central locking file cabinet in which to store the retrieved trauma registry instruments after electronic conversion.

**mHealth triage tool:** Each follow up RA assigned to each hospital will have a securely locked, encrypted, password protected computer and mobile phone dedicated solely to data entry and management. Only the follow up RA and project manager will have access to this equipment. Each RA will have a secure cabinet to store completed paper instruments until transfer to the project manager. The project manager will have an additional central locking file cabinet in which to store the retrieved trauma registry instruments after electronic conversion.

All paper forms will be scanned and labeled appropriately on Box, and hard copy forms will be retained for 5 years before being shredded.

#### 4. MONITORING AND QUALITY ASSURANCE

##### a) Real time Supervision of RAs/Study Staff

The Project Manager will supervise the activities of the mhealth follow up RAs. They will conduct biweekly checks on data collection and entry into REDCap to prevent data entry backlogs; routinely (at least monthly) retrieve completed paper forms from RAs and ensure secure storage at University of Buea Offices; Conduct biweekly checks on the scanning of paper forms for electronic storage on Box by RAs; perform biweekly data verification of 20% of project data by cross-referencing scanned paper forms with data entered on RedCap database.

The project manager will report to the study PIs and co-investigators during a standing weekly meeting. Study investigators will also conduct at least annual supervisory visits to study sites.

